5.2.1 DOSE MODIFICATION GUIDELINES FOR CARFILZOMIB

In a case of study related adverse event the clinical investigator must assess its possible relationship to carfilzomib in addition to elotuzumab and dexamethasone.

Table 7. Carfilzomib dose reduction guidelines for toxicity and dose modification			
	1 st dose reduction	2 nd dose reduction	3 rd dose reduction
70 mg/m ²	56 mg/m ²	45 mg/m ²	36 mg/m ²

The basic principle is that if a patient requires an interruption of carfilzomib of more than four weeks this study patient will be removed from study; all exceptions to this must be discussed with principal investigator. If the carfilzomib dose is reduced once, it will be continued for at least one cycle. In case of excellent toleration of this cycle, the dose level prior to reduction may be resumed by the investigator's discretion.

Table 8.

Carfilzomib dosing guidelines for treatment- emergent hematologic toxicity

Hematologic toxicity	Recommended action
Thrombocytopenia	
If platelets $\leq 30 \times 10^9/l$	If $10-30 \times 10^9/l$ without bleeding continue the same dose If evidence of bleeding or platelets $< 10 \times 10^9/l$, withhold dose until platelets return to $\geq 10 \times 10^9/l$ and/or bleeding is controlled, then resume the same dose
For each subsequent drop to $\leq 30 \times 10^9/l$	If $10-30 \times 10^9/l$ without bleeding continue at the same dose If evidence of bleeding or platelets $< 10 \times 10^9/l$, withhold dose until platelets return to $\geq 10 \times 10^9/l$ and/or bleeding is controlled, then resume at 1 dose reduction.
Neutropenia	
If ANC $\leq 0.75 \times 10^9/l$	If ANC $0.5-0.75 \times 10^9/l$, continue at the same dose If ANC $< 0.5 \times 10^9/l$, withhold dose until ANC returns to $\geq 0.5 \times 10^9/l$, then resume at the same dose.
For each subsequent drop to $\leq 0.75 \times 10^9/l$	If ANC $0.5-0.75 \times 10^9/l$, continue at the same dose If ANC $< 0.5 \times 10^9/l$, withhold dose until ANC returns to $\geq 0.5 \times 10^9/l$, then resume at 1 dose reduction
Neutropenic fever	If ANC $< 0.5 \times 10^9/l$, and single temperature $> 38.5^\circ\text{C}$ or temperature $> 38.0^\circ\text{C}$ more than one hour, withhold dose until ANC returns to baseline level, then resume at the same dose.

ANC = absolute neutrophil count.

Helsinki University Hospital Comprehensive Cancer Center Hematology
Clinical study protocol NMSG#24/15

Conditions not requiring dose reduction of carfilzomib

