- Grade 3 nausea, vomiting or diarrhea, unless persisting more than 3 days with adequate treatment of antiemetics or antidiarrheal agents
- Grade 3 dexamethasone-related hyperglycemia
- Grade 3 fatigue, unless persisting for > 14 days
- Alopecia

Table 9. Carfilzomib dosing guidelines for nonhematologic toxicity

Nonhematological toxicity	Recommended action
Renal dysfunction	
Serum creatinine equal to or greater than 2 x baseline, or CrCl < 15 ml/min, or decreases to ≤ 50% of baseline or need for dialysis	Withhold dose and continue monitoring the renal function If attributable to carfilzomib, resume when renal function has recovered to within 25% of baseline, start at 1 dose level reduction If not attributable to carfilzomib, dosing may be resumed at the discretion of the physician Patient will be withdrawn from study in case of permanent dialysis need
≥ grade 3 elevation in liver function tests	Withhold dose and resume at 1 dose reduction level when toxicity has recovered to baseline
Grade 3 infection	Withhold carfilzomib until infection resolves and resume at the same dose
Congestive heart disease	Any subject with symptoms of congestive heart failure, whether or not drug related, must have the dose held until return to baseline, after which treatment may continue at a reduced dose, or consider discontinuation of study protocol. If no recovery in 4 weeks, patient must be withdraw.
Left ventricular ejection fraction	
For resting LVEF < 40% or reduction of LVEF to < 55% if the drop is greater than 20% form baseline	Withhold until LVEF returns to > 40% or, if held due to a drop to < 55%, to within 15% of baseline and resume at 1 dose reduction.
Other grade 1 or 2 nonhematologic toxicity	Continue at the same dose
Any other drug-related nonhematologic toxicity ≥ grade 3	If attributable to carfilzomib, withhold dose Resume at 1 dose reduction when toxicity has resolved to grade 2 or less or to baseline If tolerated, the reduced dose may be escalated to the previous dose at the discretion of the physician
PRES: posterior reversible encephalopathy syndrome; headache, altered mental status,	Stop carfilzomib and study treatment and the patient is withdrawn from study. In visual or

Helsinki University Hospital Comprehensive Cancer Center Hematology
Clinical study protocol NMSG#24/15

seizures, visual loss, hypertension	neurological symptoms	neuroradiological imaging is recommended.
-------------------------------------	-----------------------	---

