7.6 Potential Drug-Induced Liver Injury (DILI)

Wherever possible, timely confirmation of initial liver-related laboratory abnormalities should occur prior to the reporting of a potential DILI event.

Helsinki University Hospital Comprehensive Cancer Center Hematology
Clinical study protocol NMSG#24/15

All occurrences of potential DILIs meeting the defined criteria must be reported as SAEs.

Potential drug induced liver injury is defined as

1. AT (ALT or AST) elevation > 3 times upper limit of normal (ULN), AND

Total bilirubin > 2 times ULN, without initial findings of cholestasis (elevated serum alkaline phosphatase), AND

2) No other immediately apparent possible causes of AT elevation and hyperbilirubinemia, including, but not limited to, viral hepatitis, pre-existing chronic or acute liver disease, or the administration of other drug(s) known to be hepatotoxic.

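### Table 9 states no carfilzomib hold for an event that meets the section 7.6 potential-DILI criteria while every liver test is below grade 3

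*Protocol*

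**What the plan says.** Three parts of the protocol bear on this.

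- **Section 5.2.1, Table 9.** The action column is headed "Recommended action". The single liver row is triggered by "≥ grade 3 elevation in liver function tests"; it withholds carfilzomib and restarts one dose level lower once values are back to baseline. A catch-all row withholds for any other drug-related nonhematologic toxicity, also only from grade 3 and only if attributable to carfilzomib. The row labelled "Other grade 1 or 2 nonhematologic toxicity" keeps the dose unchanged. DILI is not mentioned in the table.
- **Section 7.6.** Potential DILI requires "AT (ALT or AST) elevation > 3 times upper limit of normal (ULN), AND" "Total bilirubin > 2 times ULN, without initial findings of cholestasis", together with no other immediately apparent cause. The stated consequence is: "All occurrences of potential DILIs meeting the defined criteria must be reported as SAEs". No hold, reduction or stop is given.
- **Sections 7 and 7.1.** Section 7 obliges investigators to apply the dose-adjustment guidelines to every patient and to take exceptional issues to the principal investigator. Section 7.1 has the intensity of each SAE graded by CTCAE v4.0, used as a guideline where possible.

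For elotuzumab, a liver rule with the same grade 3 threshold appears only in the background text (section 1.4.1, Hepatic Impairment). The only toxicity stop in section 5.3 is a grade 4 infusion reaction.

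**The concern.** Section 7.2 classes potential DILI as an important medical event that must be handled as an SAE. The dosing table does not pick up that classification. A patient whose transaminases and bilirubin rise together, with no apparent other cause, could receive the next full carfilzomib dose while the event is being evaluated. One site might hold and another might not, and both could say that they followed the protocol.

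Two comparisons make the gap look unintended. Section 4.2.1 admits only patients with bilirubin below 1.5 x ULN and ALT and AST below 3 x ULN, so anyone meeting section 7.6 exceeds both entry limits yet may have no stated hold once on treatment. Table 9 also withholds first and asks about cause afterwards for renal dysfunction, and it withholds for symptoms of heart failure whether or not they are drug related. The liver has a defined serious-injury screen that is not linked to dosing.

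**Working it through.** No sample size, power or error rate is involved. The check compares two sets of thresholds.

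**Inputs**
- Section 7.6: ALT/AST > 3 x ULN and total bilirubin > 2 x ULN.
- Table 9: liver hold from grade 3.
- Grading scale: CTCAE v4.0 (sections 7.1 and 9.2). The cut-offs are not printed in the protocol, so they are assumptions here.

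**Step 1: the window.** Let grade 3 start above a x ULN for transaminases and above b x ULN for bilirubin. An event meets section 7.6 with both tests below grade 3 when

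3 < ALT/AST ≤ a and 2 < bilirubin ≤ b,

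which is possible whenever a > 3 and b > 2.

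| Assumed (a, b) | ALT/AST, x ULN | Bilirubin, x ULN |
|---|---|---|
| (5, 3), main assumption | above 3, up to 5 | above 2, up to 3 |
| (4, 2.5), illustrative | above 3, up to 4 | above 2, up to 2.5 |
| a ≤ 3 or b ≤ 2 | empty | empty |

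**Step 2: an example against each row.** Take ALT 4 x ULN and bilirubin 2.5 x ULN, no cholestasis, no other cause, under (5, 3).
- Section 7.6: met (4 > 3 and 2.5 > 2), so an SAE report is due.
- Liver row: not triggered (4 ≤ 5 and 2.5 ≤ 3).
- Catch-all row: not triggered if grading is test by test. It is triggered if the site grades the combined event 3 or higher and attributes it to carfilzomib.
- Grade 1 or 2 row: read literally, same dose. If its first word is taken to exclude liver tests because they have their own row, the table is silent.

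Only the event-level grading route leads to a hold, and the protocol prescribes no grade for the event.

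**Step 3: dose at stake.** Table 1 schedules chemistry or a safety lab, including ALT and bilirubin, for days 1, 8 and 15 of cycles 1-8 and for days 1 and 15 from cycle 9. Table 6 gives carfilzomib on those same days. Each dose thus has its own lab, and the exposure before the next check is one dose: usually 70 mg/m², or 56 mg/m² for patients 1-5 in cycles 1-2, and less after a Table 7 reduction.

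**The case against.** The strongest reply is that the two sections do different jobs. Section 7.6 is a provisional case definition for safety reporting, Table 9 is a dosing guide, and both can be followed at once. A grade 3 liver threshold is a legitimate choice and matches the elotuzumab text. The table offers recommendations, and section 5.2.1 says that "the clinical investigator must assess its possible relationship to carfilzomib in addition to elotuzumab and dexamethasone". Section 4.2.4 allows dose reduction for intolerability at the investigator's decision, and section 4.2.3 allows withdrawal for an adverse event. SAEs are reported within 24 hours and followed to resolution or stabilization (section 7.2), sites must alert the principal investigator at once to severe events (section 10.1), and an external safety board reviews events (section 8). Section 7.1 grades each SAE, which opens a route to the catch-all hold.

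Much of this stands. A reader might infer that the protocol contradicts itself, or that it orders redosing in suspected liver injury. The documents support neither: the sections are compatible, and continuing the dose follows only from a literal reading of a row that may not be meant for liver tests.

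What does not stand is that these provisions close the gap. They are discretionary or concern reporting, and none states a hold. The board discusses events every 6-8 months, whereas in cycles 1-8 the next dose within a cycle can be a week away. Section 7 also makes adherence to the dose guidelines obligatory, which weakens the argument that they are only recommendations.

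**Conclusion.** The point holds as a narrow patient-safety gap, worth correcting when the protocol is next amended. It affects no endpoint, sample size or analysis.

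It rests on the assumption that CTCAE grade 3 starts above 3 x ULN for transaminases and above 2 x ULN for bilirubin. The width of the window depends on the exact cut-offs, but its existence needs only those two inequalities. It also depends on sites grading by individual test, or grading the combined event below 3.

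Two larger estimates of its size are tempting and should not be used.
- **A full cycle of exposure.** A reader might count 3 x 70 = 210 mg/m² per cycle. That supposes three doses without a look at the liver tests, whereas a lab is scheduled before each dose.
- **Four patients.** A reader might take Table 5's ceiling of 1 in 10 for liver problems and compute 0.10 x 40 = 4. That is one cell of the table. Liver failure and cholestasis sit in another column, raised bilirubin sits in the row for tests, and the figures concern carfilzomib, not this combination. The number who would fall in the window cannot be derived from it; all that can be said is that few are expected.

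**What to change.** Add a row to Table 9 along these lines:

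*Event meeting the section 7.6 criteria with all liver tests below grade 3: withhold carfilzomib pending evaluation. If attributable to carfilzomib, or if no other cause is found, restart one dose level lower once recovered to baseline. If another cause is found, restart is left to the physician's judgement.*

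The last clause follows the renal row, which already says "If not attributable to carfilzomib, dosing may be resumed at the discretion of the physician". Limiting the new row to tests below grade 3 matters. A row applying at any grade would overlap the existing liver row and put two sets of restart terms on one event. The existing row should go on governing any test at grade 3 or higher. By Table 7 one level lower means 70 to 56, 56 to 45 or 45 to 36 mg/m²; where there is no lower level, the principal investigator decides. Optionally, state the same hold for elotuzumab in section 5.3.

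The cost is one table row and, if wanted, one sentence. No new tests are needed, since ALT, alkaline phosphatase and bilirubin are already scheduled (Table 1, section 6.4). The downside is an occasional held or reduced dose, sometimes in a patient whose event proves to have another cause. A hold of more than four weeks would fall under the existing removal rule in section 5.2.1, with its provision for exceptions discussed with the principal investigator.

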1.4.2 Carfilzomib

Carfilzomib is a second-generation selective and irreversible proteasome inhibitor, which as a single agent has demonstrated clinical activity in patients with relapsed/refractory multiple myeloma. The proteasome is an intracellular protease complex that is responsible for the ubiquitin-dependent turnover of cellular proteins in normal and malignant cells. An important role of the proteasome in the context of multiple myeloma is the regulation of nuclear factor NF- κ B. The chymotrypsin-like domain of the proteasome has been shown to be

Helsinki University Hospital Comprehensive Cancer Center Hematology
Clinical study protocol NMSG#24/15

the rate-limiting step of proteolysis in vitro and in vivo Bortezomib was the first proteasome inhibitor to be introduced in myeloma treatment and has gained a central role in treatment of several treatment lines in the era of novel drugs. However, it has a high incidence of peripheral neuropathy causing cessation of treatment in a proportion of patients, and resistance development along the time is a rule. The side effect profile of carfilzomib is milder than with bortezomib, and especially the incidence of neuropathy is significantly lower. The most common side effects are cytopenias, in particular thrombocytopenia and anemia, fatigue, nausea, dyspnea, diarrhea and pyrexia. (incidence $\geq 30\%$). However, most of these side effects were mild and only the cytopenias were of grade 3 or 4 in more than 10% of the patients. Some severe side-effects have rarely been observed in phase 2 trials. Thus, cardiac failure events (e.g., cardiac failure congestive, pulmonary edema, ejection fraction decreased) were reported in 7% of patients. Pulmonary arterial hypertension was reported in 2% of patients. Tumor lysis syndrome occurred following carfilzomib administration in $< 1\%$ of patients (For FDA approved highlights of prescribing information:

http://www.accessdata.fda.gov/drugsatfda_docs/label/2012/202714lbl.pdf).

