<1% of patients. The recommendation is that patients are routinely evaluated for hypertension.

Pulmonary hypertension: Pulmonary hypertension has been reported in approximately

1% of patients. The recommendation is to evaluate pulmonary symptoms, stop carfilzomib until resolved or returned to baseline, and consider whether to restart carfilzomib.

Pulmonary toxicities: Interstitial lung disease (including pneumonitis), acute

respiratory failure and ARDS have been reported in <1% of patients. The recommendation is to evaluate pulmonary symptoms, stop carfilzomib until resolved or returned to baseline, and consider whether to restart carfilzomib.

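### Table 9 has no pulmonary row, so its residual rows conflict with the protocol's own instruction to stop carfilzomib for pulmonary hypertension and pulmonary toxicity

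*Protocol*

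**What the plan says.** Two parts of the Protocol govern carfilzomib dosing when a pulmonary event occurs.

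**Section 1.4.2.2, new safety information on carfilzomib.** The same instruction is given for pulmonary hypertension and for pulmonary toxicities (interstitial lung disease including pneumonitis, acute respiratory failure, ARDS): "The recommendation is to evaluate pulmonary symptoms, stop carfilzomib until resolved or returned to baseline, and consider whether to restart carfilzomib". No grade threshold is attached, and no requirement that the event be attributed to carfilzomib.

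**Section 5.2.1, Table 9.** The named rows are renal dysfunction, liver function tests, grade 3 infection, congestive heart disease, left ventricular ejection fraction and PRES. None is pulmonary. Two residual rows take everything else:

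- "Other grade 1 or 2 nonhematologic toxicity": dosing continues unchanged.
- Any other drug-related non-hematologic toxicity of grade 3 or higher: "If attributable to carfilzomib, withhold dose", then "Resume at 1 dose reduction when toxicity has resolved to grade 2 or less or to baseline". Return to the previous dose is later allowed at the physician's discretion.

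Section 7 requires investigators to follow the dose reduction and adjustment guidelines in every patient and refers exceptional issues to the principal investigator.

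**The concern.** A site dosing from Table 9 could keep a patient with grade 1-2 pulmonary hypertension or pneumonitis on full-dose carfilzomib. It could also restart a patient whose grade 3 event has improved only to grade 2. In both cases the protocol's own notice says the drug should be off. The default written in the dosing table is the less cautious of the two rules, in a combination for which section 10.1 says there is no prior experience.

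The omission also does not fit the table's own pattern. PRES has a row, although Table 5 lists it as rare (up to 1 in 1000). Heart failure is handled strictly: "Any subject with symptoms of congestive heart failure, whether or not drug related, must have the dose held until return to baseline". Pulmonary hypertension, which Table 5 lists as common, gets only the general default.

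**Working it through.** **Step 1. Which Table 9 row applies?** If the event is a grade 3 infection, the infection row governs ("Withhold carfilzomib until infection resolves and resume at the same dose"). If it presents as heart failure, the congestive heart disease row governs. Otherwise pulmonary hypertension, interstitial lung disease/pneumonitis, acute respiratory failure and ARDS fall to the residual rows.

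**Step 2. The two texts side by side.**

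| Situation | Section 1.4.2.2 notice | Table 9 residual rows | Result |
|---|---|---|---|
| Grade 1-2 | Stop | Same dose | Conflict |
| Grade ≥3, attributed to carfilzomib, at onset | Stop | Withhold | Agree |
| Same event, improved to grade 2, neither resolved nor at baseline | Stay off | Restart one level lower | Conflict |
| Grade ≥3, not attributed to carfilzomib | Stop | Silent | Gap, not a conflict |

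For a patient on 70 mg/m², the first conflict is 70 mg/m² against no dose. The second is 56 mg/m² (the first reduction in Table 7) against no dose.

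**Step 3. How many patients could have such an event?** The protocol has no figure of its own to reproduce here. Inputs:

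- Pulmonary hypertension: about 1% (section 1.4.2.2) or 2% (section 1.4.2: "Pulmonary arterial hypertension was reported in 2% of patients").
- Pulmonary toxicities: under 1% (section 1.4.2.2: "respiratory failure and ARDS have been reported in <1% of patients").
- N = 40.

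Combined rate:

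- Low: 1% + about 0 = about 1%.
- High: 2% + under 1% = just under 3%.

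Expected patients, N × p:

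- 40 × 0.01 = 0.4
- 40 × 0.03 = 1.2

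Chance of at least one, 1 − (1 − p)^40:

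- 1 − 0.99^40 = 0.331
- 1 − 0.97^40 = 0.704

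Table 5 places pulmonary hypertension in a band of up to 1 in 10. That is a category limit rather than a rate, so it is not used; at the limit it would give 40 × 0.10 = 4 patients.

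**The case against.** The best counter-argument is that a specific instruction overrides a general one. The residual rows are catch-alls, and the notice is specific and flagged as important. Read that way, the texts fit together: stop for the named pulmonary events and use Table 9 for the rest. Section 7 names no table, and a recommendation to stop can itself be read as a dose guideline. The notice may also presuppose a symptomatic, clinically significant event, since it begins with evaluating symptoms. It does not define resolution, so Table 9 could be supplying the working threshold.

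There are other safeguards. Acute diffuse infiltrative pulmonary disease is among the exclusions (section 4.2.2). The responsible physician may change therapy (section 4.2.3). Lung function tests are available if clinically needed (section 6.7), SAEs are reported within 24 hours (section 7.2), and an external board discusses adverse events every 6-8 months (section 8).

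Parts of this stand. The notice is a recommendation and Table 9 also gives recommended actions, so a careful investigator could follow the notice. The 33% to 70% measures any such event, not the disputed situations, and is therefore only an upper bound on the chance that a conflict arises. The documents also do not show that grade 1-2 acute respiratory failure or ARDS would occur, so the first situation matters mainly for pulmonary hypertension and pneumonitis.

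The rest does not remove the problem. The specific-over-general rule is stated nowhere. Section 5.2.1 is titled as the carfilzomib dose modification guidelines, so it is the natural referent of section 7. Table 9 does not point back to the notice. Discretion and periodic review do not tell a site which written rule is meant on the day of dosing.

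**Conclusion.** The concern holds. As written, Table 9 contradicts the section 1.4.2.2 notice in two situations: grade 1-2 pulmonary events, and carfilzomib-attributed events of grade 3 or higher that have improved only to grade 2. It is silent on unattributed events of grade 3 or higher.

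The expected number of affected patients is small, at most about one in this trial. That rests on rates from other carfilzomib studies carrying over to 70 mg/m² weekly with elotuzumab, and on adding a pulmonary hypertension rate and a pulmonary toxicity ceiling from different sources at the upper end. The consequence for an individual patient could be serious, and the correction is cheap, so it should be made. The ORR estimate and its confidence interval are not affected.

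**What to change.** Add a Table 9 row for pulmonary hypertension and for interstitial lung disease/pneumonitis, acute respiratory failure and ARDS. It should repeat the section 1.4.2.2 instruction: evaluate the symptoms, hold carfilzomib until resolution or baseline, then decide whether to restart and document the decision. State that this row takes precedence over both residual rows. If the sponsor intends a grade or attribution threshold, write it in both places.

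The cost is a one-row protocol amendment and a letter to sites, plus held doses in about one patient (0.4 to 1.2 expected). A slowly resolving event could reach the section 5.2.1 rule that removes a patient after more than four weeks without carfilzomib. From Table 6, four weeks is 3 × 70 = 210 mg/m² in cycles 3-8, or 2 × 70 = 140 mg/m² from cycle 9. That section already allows exceptions by discussion with the principal investigator, so a responding patient with a mild event need not be lost automatically.
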